2.4 Sample Size Justification

The target sample size for the time and motion evaluation undertaken as part of this study is 240 ERT episodes, including 60 ERT episodes (30 for agalsidase alfa and 30 for agalsidase beta) in each participating country. Ideally, a maximum of two ERT administration episodes will be observed per patient; as such, at least 30 patients are expected to be enrolled in each country. For countries with limited FD patient numbers, a review of episodes of care observed will be completed on an ongoing basis. It may be determined that it is possible to observe three

episodes per patient in these circumstances, however only two episodes will be observed per patient wherever possible.

For the questionnaire evaluation, approximately 120 patients and 20 caregivers will be expected to fill questionnaire sets (approximately 30 patients' and 5 caregivers' questionnaire sets per country).

2.5 Analysis for descriptive endpoints

This study is designed to be descriptive in nature; there is no *a priori* hypothesis to be tested and therefore no comparisons between patient subgroups or treatments will be made. Distributions and descriptive statistics of central tendency (medians and arithmetic or geometric means) and dispersion (standard deviation [SD], interquartile range [IQR], range) will be presented for quantitative variables. Categorical variables will be described with frequencies and percentages; where appropriate, distributions, modes, medians, IQR and range will be reported. Where appropriate, 95% confidence intervals (95% CI) will also be presented for means and estimates of proportions. Ordinal variables will be evaluated using either frequencies and percentages or medians and IQR or both depending on the number of possible values for the variable.

Analysis for validated instruments will adhere to the licensed scoring manual. Item and domain scores (if relevant) will be presented.

All percentages will be reported to the nearest whole number; therefore, in reporting study results in tables, figures and associated text, percentages may not add up to 100% due to rounding. For total group/subgroup sizes of less than 10, percentages will not be reported, except under exceptional circumstances. Consideration will be given during data analysis as to whether reporting any of the planned analyses may identify individuals from combinations of variables occurring in very small groups; to preserve participant anonymity such results may be suppressed in the study report and any materials intended for publication.

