9.1.1 Prospective time and motion study

Patients with FD attending the hospital or treatment centre for administration of a single dose of ERT (with agalsidase alfa or agalsidase beta) during the prospective recruitment period will be observed by an independent researcher or a member of their care team for the duration of their episode of care. The observer will record the HCP time associated with all activities relating to the preparation and administration of ERT (including the pre-infusion clinical assessment and post-administration documentation). It is possible that a single patient may present to the hospital or treatment centre for administration of ERT multiple times within the recruitment period (when they return for follow-up treatment), but repeated observation of the same patient will ideally be capped at two episodes of care per patient, to minimise bias from multiple observations of patients with atypical resource use. For countries with limited FD patient numbers, a review of episodes of care observed will be completed on an ongoing basis. It may be determined that it is possible to observe three episodes per patient in these circumstances, however only two episodes will be observed per patient wherever possible. For patients who are eligible to be observed more than once, initial consent for observation of up to three episodes of care will be obtained, and will be confirmed verbally by their HCP before the second or third episode of care is observed.

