9.8 Study size

This study aims to recruit sufficient patients to record 30 episodes per treatment per country. Given this, the number of patients recruited will range from 15 to 30 per treatment per country. To evaluate the value of the sample estimates of the population that this sample size will allow for, it will be assumed pessimistically that each patient will have one measurement; the estimates once the study is carried out will therefore have higher precision than calculated below.

The anticipated length of time for pre and post-administration activities and infusion for each treatment utilised estimates from the research of Guest et al.¹⁷ alongside clinical opinion sourced from sites in the countries of study; it was estimated that pre-administration processes would always take between 10-30 minutes, post-administration processes would take between 15-30 minutes, infusion of agalsidase alfa takes between 40 to 60 minutes and infusion of agalsidase beta would take between 90 to 180 minutes. To anticipate the precision of estimates given the sample size above, it was estimated that these times would follow a normal distribution within these ranges (as a result, the mean could be estimated by taking the middle value of the range and the standard deviation roughly approximated accordingly).

It is important to account for the fact that Fabry disease is rare and that the sample collected will represent a large proportion of the total population with disease. For instance, in the US, it was estimated that there were only approximately 7700 patients in total out of a population of about 323 million in 2016, which suggests that only 0.0024% have the disease. The estimated number of Fabry disease patients in other countries can be calculated from the prevalence of the disease in the US, by multiplying the expected proportion of the population with the disease (assuming that the prevalence is similar in the US to other countries) with the estimated total population (Brazil, Japan, Taiwan and Turkey therefore could have an estimated patient population of about 5015, 3033, 573 and 1934 patients respectively based on estimates of total population of 210 million, 127 million, 24 million and 81 million patients respectively²⁴). Accounting for this, the estimated precision of estimates of time at different sample sizes for the largest and smallest countries in the study by population can be seen in the table below.

Table 5. Sample size estimations

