2.1 Populations for analysis

Patients with FD who are receiving ERT and their caregivers from approximately 12 specialist centres in four countries (Taiwan, Turkey, Brazil and Japan) will form the sample for this study. In total, this study will have 240 ERT episodes, which includes 60 ERT episodes (30 for agalsidase alfa and 30 for agalsidase beta) in each participating country. Ideally, a maximum of two ERT administration episodes will be observed per patient; as such, at least 30 patients are expected to be enrolled in each country. For countries with limited FD patient numbers, a review of episodes of care observed will be completed on an ongoing basis. It may be determined that it is possible to observe three episodes per patient in these circumstances, however only two episodes will be observed per patient wherever possible.

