2.2 Key definitions

Episode of care: An episode of care is an element or part of the care or treatment pathway which is being studied or measured. For the purpose of this study, an episode of care will constitute all healthcare professional (HCP) activities involved in the preparation and administration of a single dose of enzyme replacement therapy (ERT) with agalsidase alfa and agalsidase beta, including ERT (and pre-medication) preparation, pre- and post-administration assessment, pharmacy and clinic activities, and any follow up activities.

Caregiver: in the context of this study a caregiver is defined as an individual aged 18 years or over who has a personal relationship with and provides informal (unpaid) care, support or assistance to someone diagnosed with Fabry Disease, and accompanies them to the hospital or treatment centre for ERT administration on one or more occasion during the study data collection period. For example, this may be a parent, spouse/ partner, son/ daughter, other relative, neighbour or friend.

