2.3 Missing Data

Where dates are ambiguous because of missing day and/or months, standard imputation will be applied: where day is missing the 15th of the month will be assumed; where both day and month are missing the 1st July will be assumed.

For other missing data, the affected analyses will be conducted using only the results of those patients/episodes with data available and the number included in each analysis will be stated.

The number of patients or caregivers with data missing will be reported for each study variable.

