2.6 Analysis of the primary objectives

Objective 1	To quantify the total time spent by HCPs in the preparation and administration of a single dose of ERT (with agalsidase alfa and agalsidase beta) in patients with FD.
Endpoint and variables required	Description of analytical approach
The total time spent by HCPs (physician / nurse / nurse assistant or healthcare assistant / pharmacist / pharmacy assistant / other) in the preparation and administration of a single dose of ERT in patients with FD	The total time spent will be treated as quantitative variables and will be summarized with mean, sd etc, as per described in section 2.5. The summary statistics will be produced separately for each country and by ERT product (agalsidase alfa or agalsidase beta).
Episode setting (hospital / infusion centre / primary healthcare centre / primary healthcare centre (preparation and set-up) with home infusion) / other (specify)	The frequency and percentages will be provided for each of these categorical variables.
ERT product administered: agalsidase alfa (Replagal®, Shire or biosimilar) or agalsidase beta (Fabrazyme®, Sanofi Genzyme or biosimilar) 
 ○ ERT dose administered. ○ Pre-medications administered 	
Secondary Endpoints Summary measures of the time spent by HCPs on the following tasks associated with the preparation and administration of a single dose of ERT (with agalsidase	The total time will be calculated by summing the difference in start and end time of these activities. This will be summarized using mean, sd, median and IQR as per section 2.5.

alfa or agalsidase beta) in patients with FD:
	

Pre-administration patient consultation:
 
 ○ Time patient arrived ○ Time patient left clinic 	
Time patient left – Time patient arrived
 
End time – Start time

Start and end time of patient consultation with HCP for pre-treatment assessment.
	
End time – start time

Start and end time of prescription writing (if additional to consultation time with patient).
	
End time – start time

Start and end time of pre-administration clinical documentation (if additional to consultation time with patient).
	

Infusion (and pre-medication) preparation activities:
	
End time – start time

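### The SAP gives no variance method for repeat episodes from one patient, so a 95% CI for HCP time that treats episodes as independent would be too narrow

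*SAP*

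**What the plan says.** SAP 2.2 defines the unit of observation as the episode of care, meaning the HCP work around one dose. For total HCP time, SAP 2.6 states: "The total time spent will be treated as quantitative variables and will be summarized with mean, sd etc, as per described in section 2.5", separately by country and product. SAP 2.5 lists means, medians, SD, IQR and range and adds, where appropriate, that "95% confidence intervals (95% CI) will also be presented for means and estimates of proportions". It gives no formula.

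SAP 2.1 and 2.4 set 30 episodes per country-by-product cell. They cap observation at two episodes per patient, with three possible where patients are few, although "only two episodes will be observed per patient wherever possible". SAP 2.4 concludes: "as such, at least 30 patients are expected to be enrolled in each country". Protocol 9.8 adds that "the number of patients recruited will range from 15 to 30 per treatment per country". The reason for the cap, in Protocol 9.1.1, is "to minimise bias from multiple observations of patients with atypical resource use".

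Neither document mentions a clustered standard error, a mixed model, an analysis of patient means or a rule of one episode per patient. Protocol 9.9.4 plans no sensitivity analyses. The SAP shell tables are still to be confirmed.

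**The concern.** At the stated minimum of 30 patients per country, 60 episodes means 60/30 = 2 per patient on average. Repeats are therefore the expected case. Two infusions of the same patient, often at the same site and under the same routine, are likely to take similar time. The protocol's own reason for the cap recognises that patients differ in resource use, and such differences produce positive within-patient correlation.

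If the analyst applies the usual software default, SD/√30 with t on 29 degrees of freedom, each repeat counts as a full new observation. The study tests no hypothesis and Protocol 9.8 justifies its size by the width of confidence intervals, so the interval is its main statement of precision. The protocol also foresees use of the data in HTA submissions. At stake is an interval on the primary endpoint that claims more precision than the data hold.

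**Working it through.** **Step 1: reproduce the plan's own figure.** Table 5 (Protocol 9.8) assumes one measurement per patient. The activity ranges sum to 65–120 min overall for alfa (10+15+40 to 30+30+60) and 115–240 min for beta (10+15+90 to 30+30+180). The protocol gives no SD. Taking SD = range/4 gives 55/4 = 13.75 and 125/4 = 31.25 min. The half-width is t(0.975, n−1) × SD/√n × √((N−n)/(N−1)), with N = 5015 for Brazil.

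- Beta, n = 15: 2.145 × 31.25/√15 × √(5000/5014) = 17m17. Table 5: 160m13 to 194m47, half-width 17m17.
- Beta, n = 30: 2.045 × 31.25/√30 × √(4985/5014) = 11m38. Table 5: 165m52 to 189m08, half-width 11m38.
- Alfa: 7m36 at n = 15 and 5m07 at n = 30, both as in Table 5.

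The SD rule fits, and the table counts patients.

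**Step 2: the effect of repeats on the width.** With m episodes from each of k patients (km = 30) and intraclass correlation ρ, the variance of the mean is SD²/30 × (1 + (m−1)ρ), with k−1 degrees of freedom. No finite population correction is used from here on.

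- Episodes taken as independent: 2.045 × 31.25/√30 = 11m40 (beta); 5m08 (alfa).
- 15 × 2, ρ = 0.5: 2.145 × 31.25 × √(1.5/30) = 14m59 (beta); 6m36 (alfa). Ratio to the independent interval: 1.28.
- 10 × 3, ρ = 0.5: 2.262 × 31.25 × √(2/30) = 18m15 (beta); 8m02 (alfa). Ratio: 1.56.

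**Step 3: coverage.** Simulated with normal data, a patient random effect, no site differences and 100,000 replicates. The figures are the coverage of the nominal 95% t-interval on 30 episodes.

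| Patients in cell | ICC 0.1 | 0.2 | 0.5 | 0.8 |
|---|---|---|---|---|
| 30, once each | 95% | 95% | 95% | 95% |
| 25 (5 seen twice) | 94.6% | 94.3% | 93.1% | 91.8% |
| 20 (10 seen twice) | 94.3% | 93.5% | 91.0% | 88.5% |
| 15, twice each | 93.7% | 92.7% | 89.0% | 84.8% |
| 10, three times each (exceptional) | 92.6% | 90.3% | 82.8% | 75.8% |

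**Step 4: the replacement interval.** Keep the mean ȳ over the n episodes. Take SE = √[k/(k−1) × Σ over patients of (sum of that patient's residuals from ȳ)²]/n, with t on k−1 degrees of freedom. With one episode per patient, k = n and this reduces to s/√n, the ordinary interval. Its coverage in every repeat row above is 94.6–95.0%. At 15 × 2 its average width is 1.09, 1.14, 1.29 and 1.42 times that of the ordinary interval at ICC 0.1, 0.2, 0.5 and 0.8.

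**Step 5: sites.** Protocol 9.2 expects 2–3 sites per country. For 15 × 2 with total correlation 0.5, of which 0.1, 0.2 or 0.3 is between sites:

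| Target of the interval | Sites | Ordinary | Patient-clustered |
|---|---|---|---|
| Mean of the participating sites | 3 | 90.8 / 92.5 / 94.4% | 95.9 / 96.6 / 97.4% |
| Mean of the participating sites | 2 | 90.6 / 91.9 / 93.7% | 95.8 / 96.2 / 96.8% |
| Wider population of sites | 3 | 80.1 / 72.2 / 66.0% | 88.8 / 82.2 / 75.8% |
| Wider population of sites | 2 | 75.2 / 65.0 / 57.0% | 84.9 / 75.2 / 66.5% |

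**The case against.** The strongest reply is that the SAP nowhere says episodes are independent, promises intervals only where appropriate, and describes a study without tests or comparisons. All of that is true. A reader might infer that the SAP prescribes the wrong interval; the text supports only that it prescribes none. The gap remains, because silence leaves the choice to the analyst and the default is the narrow interval.

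A reader might also infer that the sample-size reasoning fails. It does not. Table 5 deliberately counts one measurement per patient and shows 15 to 30 patients. At 15 × 2 and ICC 0.5 the beta half-width of 14m59 lies between its 30-patient and 15-patient columns (11m38 and 17m17). For the same reason the 15-patient column is not the equivalent of 15 × 2. It is a conservative bound, reached only as the ICC approaches 1. Only the exceptional 10 × 3 cell, below the range given in Protocol 9.8, can exceed it (18m15 at ICC 0.5).

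Extending the point to proportions is tempting too. SAP 2.6 gives the episode-level categorical variables only frequencies and percentages, and the work-absence proportions come from one questionnaire set per participant. No specific interval needs replacing there.

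Finally, patient clustering is not a complete answer. Protocol 9.1 expects results to generalise within each country, and Protocol 9.11 expects centres to differ. For that wider target the clustered interval covers only about 66–89% in the site scenarios. For the participating sites alone it over-covers somewhat, and the ordinary interval is sometimes nearer 95%. This part of the objection stands and belongs in the fix.

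**Conclusion.** The concern holds for the reported confidence interval of mean episode-level HCP times, and for nothing wider. Where patients contribute repeats and within-patient correlation is positive, a t-interval on episodes under-covers. At 15 × 2 the coverage is about 94/93/89/85% at ICC 0.1/0.2/0.5/0.8. At the exceptional 10 × 3 it is about 93/90/83/76%. With 25 patients it stays at about 92% or more, and with one episode per patient it is 95%.

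These figures rest on an assumed ICC, normal data and no site differences. The omission itself is certain; the size of its effect is not. Means are unaffected, and the expected SD falls by only about 2% at most at 15 × 2 (√(28/29) = 0.98 at ICC 1). Questionnaire outcomes are unaffected, since each summary uses one value per participant. The point should be fixed before analysis, because it concerns the primary endpoint in its expected configuration and the remedy is cheap.

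**What to change.** Add one paragraph to SAP 2.5, referred to from 2.6:

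- Any 95% CI for the mean of an episode-level time-and-motion variable keeps the mean over episodes. It uses the patient-cluster-robust standard error of Step 4 (k/(k−1) correction, k = number of patients) with t on k−1 degrees of freedom.
- Each cell reports the number of patients as well as episodes. SAP 2.3 already requires that "the number included in each analysis will be stated".
- The interval is conditional on the participating sites. With 2–3 sites per country it does not cover between-site variation for a wider population, and where sites differ it is somewhat conservative for the participating sites.

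The cost is a few lines of R or Stata, since Protocol Table 4 already records patient ID for each episode. Intervals become about 1.1 to 1.4 times as wide at 15 × 2 over ICC 0.1–0.8, and stay unchanged where each patient is seen once.

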2.6 Analysis of the primary objectives

Objective 1	To quantify the total time spent by HCPs in the preparation and administration of a single dose of ERT (with agalsidase alfa and agalsidase beta) in patients with FD.
Endpoint and variables required	Description of analytical approach
The total time spent by HCPs (physician / nurse / nurse assistant or healthcare assistant / pharmacist / pharmacy assistant / other) in the preparation and administration of a single dose of ERT in patients with FD	The total time spent will be treated as quantitative variables and will be summarized with mean, sd etc, as per described in section 2.5. The summary statistics will be produced separately for each country and by ERT product (agalsidase alfa or agalsidase beta).
Episode setting (hospital / infusion centre / primary healthcare centre / primary healthcare centre (preparation and set-up) with home infusion) / other (specify)	The frequency and percentages will be provided for each of these categorical variables.
ERT product administered: agalsidase alfa (Replagal®, Shire or biosimilar) or agalsidase beta (Fabrazyme®, Sanofi Genzyme or biosimilar) 
 ○ ERT dose administered. ○ Pre-medications administered 	
Secondary Endpoints Summary measures of the time spent by HCPs on the following tasks associated with the preparation and administration of a single dose of ERT (with agalsidase	The total time will be calculated by summing the difference in start and end time of these activities. This will be summarized using mean, sd, median and IQR as per section 2.5.

alfa or agalsidase beta) in patients with FD:
	

Pre-administration patient consultation:
 
 ○ Time patient arrived ○ Time patient left clinic 	
Time patient left – Time patient arrived
 
End time – Start time

Start and end time of patient consultation with HCP for pre-treatment assessment.
	
End time – start time

Start and end time of prescription writing (if additional to consultation time with patient).
	
End time – start time

Start and end time of pre-administration clinical documentation (if additional to consultation time with patient).
	

Infusion (and pre-medication) preparation activities:
	
End time – start time


Start and end time of infusion (and pre-medication) preparation activities (note: the following activities [as appropriate] will be included in the total time, but the time for each separate activity will not be recorded]: pre-dispensing prescription review, label generation, collation of items prior to assembly, assembly of item/drug reconstitution, labelling of containers, accuracy check, prescription delivery).
	

ERT Infusion Procedure (and pre-medication) administration:
	
Time patient left – Time patient arrived

	
End time – Start time

Time patient arrived in clinic for ERT administration to begin
 
Time patient left clinic following completion of ERT administration
 
Start and end time of pre-medication administration.
 
Start and end time of ERT infusion.
 
Start and end time of HCP activity for administration of IV agalsidase alfa or agalsidase beta (including administration of pre-medications).
 
Start and end time of HCP activity for patient monitoring during agalsidase alfa or agalsidase beta infusion
 
Post-infusion administration assessment and documentation:
 
Start and end time of HCP activity for post-treatment patient assessment / monitoring.
 
Start and end time of HCP activity for completion of clinical documentation.
 
Other ERT-administration related activities
 
Start and end time of HCP activity for any other ERT administration related activities (specify).
	
End time – Start time
 
End time – Start time
 
End time - start time
 
End time – Start time

--	---

Secondary Objective 1

To quantify the total patient time, costs (i.e. out-of-pocket expenses) and work-related absence associated with attendances for the administration of a single dose of ERT (with agalsidase alfa or agalsidase beta) in patients with FD.

Summary measures of the total patient time associated with
	
--	--

attendance for the administration of a single dose of ERT (with agalsidase alfa or agalsidase beta) in patients with FD.
	
The difference between two time points will be calculated in minutes and will be summarized as per section 2.5 for quantitative variables for the following measures.

Time spent travelling to and from the hospital or treatment centre
	
Time left home – Time arrival at hospital


 ○ Time left home/work to travel to hospital or treatment centre ○ Time arrived at hospital or treatment centre 	

Time spent collecting ERT from pharmacy (where relevant)
	

Time from arrival in hospital/treatment centre to departure
	

 ○ Time from arrival in hospital/treatment centre to start of ERT infusion ○ Start and end time of ERT infusion. ○ Time left hospital or treatment centre to travel back to home/work ○ Time arrived back at home/work. 	
Time arrived – Time start of ERT
 
End time – Start time

In addition, if the patient started/delivered their ERT infusion at home following set-up at a primary healthcare centre, the following will also be included in the total patient time
	
Time arrived at home – Time left hospital

Duration of ERT infusion and any home-based post-administration activities.
 
 ○ Start and end time of ERT infusion ○ Start and end time of any post-administration activities. 	
End time – start time
 
End time – start time

Time spent travelling to and from treatment centre after ERT infusion (only if patient returned to treatment centre after ERT infusion)
 
 ○ Time left home/work to return to hospital or treatment centre (if relevant) ○ Time arrived back at hospital or treatment centre (if relevant) 	
Time left – Time arrived

Time spent at treatment centre after ERT infusion.
 
 ○ Time left hospital or treatment centre to travel back to home/work ○ Time arrived back at home/work 	
Time arrived back at hospital – Time left hospital/treatment centre
 
Time left – Time arrived back at home/ work

Summary measures of the total cost to patients (i.e. out-of-pocket expenses) associated with attendance for the administration of a single dose of ERT (to include the costs of travel / parking / subsistence / other costs).
	


 Did patient take any time off work to attend this ERT episode? If yes, number of paid / unpaid hours absent from work. Proportion of patients with work absence due to attendance for this ERT episode and number of paid / unpaid hours absent. 	
Frequency and percentages will be used to summarise the proportion of patients with work absence due to attendance for this ERT episode.
 
Number of paid/ unpaid hours from work will be summarised using mean, sd, median and IQR as per section 2.5.

Distribution of patient employment status and whether the patient attended the ERT administration visit accompanied by a relative/caregiver or alone.
	

 Patient employment status (employed full time / employed part time / unemployed / retired / student / home-maker) Were they accompanied to the hospital or treatment centre (by a relative or caregiver) or did they attend alone (accompanied / alone) 	
These categorical variables will be summarized using frequency and percentages as per section 2.5.

Costs (i.e. out-of-pocket expenses) incurred by the patient that were directly related to this ERT administration episode (to include costs of travel / parking / subsistence / any other costs).
	
Costs will be summarized using mean, sd, median and IQR as described in section 2.5.

Secondary objective 2
 
To quantify the total caregiver time costs (i.e. out-of-pocket expenses) and work-related absence associated with accompanying a patient with FD for the administration of a single dose of ERT (with agalsidase alfa or agalsidase beta).
	


Summary measures of the total caregiver time associated with accompanying a patient with FD for the administration of a single dose of ERT (with agalsidase alfa or agalsidase beta).
 
Demographics for caregiver
 
 ○ Sex ○ Age category ○ Has FD or not ○ Employment status ○ Relationship to patient ○ Type of care ○ Frequency of care 
 ○ Time left home/work to travel to hospital or treatment centre ○ Time arrived at hospital or treatment centre ○ Time of start of ERT infusion ○ Time left hospital or treatment centre to travel back to home/work ○ Time arrived back at home/work. 
If the patient started their ERT infusion at home following set-up at a primary healthcare centre, the following will also be collected (if the caregiver was involved in the activity)
 
 ○ Start and end time of ERT infusion 	
The frequency distribution and percentage for each category of the demographic variable will be given.
 
The difference between these two time points in minutes will be summarized as in section 2.5 for quantitative variables.
 
The difference between start and end time (in minutes) of these will be calculated and summary statistics will

--	---


 ○ Start and end time of any post-administration activities. ○ Time left home/work to return to hospital or treatment centre (if relevant and if accompanied by caregiver) ○ Time arrived back at hospital or treatment centre (if relevant) ○ Time left hospital or treatment centre to travel back to home/work ○ Time arrived back at home/work ○ Did caregiver take any time off work to attend this ERT episode? If yes, number of paid / unpaid hours absent from work. ○ Number of hours worked during ERT infusion (if relevant). ○ Costs (i.e. out-of-pocket expenses) incurred by the caregiver that were directly related to accompanying the patient for this ERT administration episode (to include costs of travel / parking / subsistence / any other costs). 	
be calculated by treating as quantitative variables as given in section 2.5.
 
Whether the caregiver took time off or not will be depicted as frequency and percentages. The number of paid/unpaid hours will be summarized as given in section 2.5 for quantitative variables.
 
The summary statistics for quantitative variable as in section 2.5 will be calculated.
 
The summary statistics for quantitative variable as in section 2.5 will be calculated.

--	---

Secondary objective 3

To describe patient-reported HRQoL (measured by the SF-12), wellbeing (measured by the WHO-5), levels of fatigue (measured by the bespoke Fatigue Likert scale) and work productivity (measured by the WPAI) in patients with FD treated with ERT (with agalsidase alfa or agalsidase beta).


Summary measures of patients':
 
 ○ HRQoL (SF-12 scores/ responses) ○ General wellbeing (WHO-5 scores / responses). ○ Level of fatigue (bespoke Fatigue Likert scale). ○ Levels of work impairment (WPAI scores / responses) ○ For the bespoke Fatigue Likert scale, times (hours and minutes) of completion will also be recorded. 	
Questionnaire scores and/or item responses will be reported using summary statistics, as appropriate to the questionnaire and in accordance with the licensed scoring manual / instructions for use.
 
For these scores, the total of all items in each of these will be summarized as per section 2.5 for quantitative variables. The frequency and percentages of responses for individual items will also be given. HRQoL and Who-5 will be given for baseline (the data collected during ERT infusion visit). Fatigue score will be given for baseline and the change scores from baseline to score collected at the same day evening of ERT infusion and 15 days after 1st infusion. WPAI scores will be given one at 1-7 days after infusion and change from this to 15 days after infusion.
 
The summary statistics of completion time in minutes will be calculated as per section 2.5 for quantitative variables.

---	---

Secondary objective 4

To describe work productivity (measured by the WPAI:CG) and the strain of care provision (measured by the CSI) in caregivers of patients with FD treated with ERT.

Summary measures of caregivers':
	
Questionnaire scores and/or item responses will be reported using summary statistics, as appropriate to the questionnaire and in accordance with the licensed scoring manual / instructions for use.

---	---

 ○ Levels of work impairment (WPAI:CG scores / responses). ○ Levels of strain of providing care for a patient with FD (CSI scores / responses). 	
The total scores will be summarized as per section 2.5 for quantitative variables. The individual item responses will be presented using frequency and percentages.
 
WPAI-CG will be summarized at 1-7 days after 1st infusion and change from this to 15 days after infusion.
 
CSI scores collected during ERT infusion will be summarized.

Patients' demographic and clinical characteristics (all patients)	

Summary measures of (at date of consent, unless specified):
 
 ○ Sex (male / female). ○ Age at consent. ○ Age at onset of first symptoms. ○ Levels of strain of providing care for a patient with FD (CSI scores / responses). ○ Duration of ERT treatment. ○ ERT start date. ○ ERT treatment under observation (agalsidase alfa / agalsidase beta). ○ Number of ERT infusions received in the year prior to date of enrolment, by type 	
Frequency distribution with percentages will be given.
 
Mean age with standard deviation along with other summary measures for quantitative variables as in section 2.5 will be calculated.
 
The total scores will be summarized as per section 2.5 for quantitative variables. The individual item responses will be presented using frequency and percentages.
 
The difference between ERT start date and end date will be calculated. The summary statistics for duration of ERT treatment will be given as per in section 2.5 for quantitative variables.
 
The number and percentage for the number of treatments for each type of treatment will be calculated as per section 2.5.
 
The frequency and percentages will be provided for each type of prior history.

of treatment (agalsidase alfa, agalsidase beta).
 
 ○ FD phenotype (organ involvement/complications), to include any current or prior history. ○ eGFR at enrolment (closest measurement prior and preferably within 12 months); date and measurement. ○ Urine protein levels at enrolment (closest measurement prior); date and measurement. ○ WBC alpha-galactosidase (closest prior to enrolment); date and measurement ○ LVMi at enrolment (closest measurement prior and preferably within 12 months); date and measurement. ○ FD mutation (name of mutation, if known, including: e.g. A143T) ○ Severity of FD (mild / moderate / severe) ○ Do any other relatives with whom the patient lives have FD (Yes / No / Not known). 	
Summary statistics for quantitative variables as described in section 2.5 will be provided for these variables.
 
Frequency distribution along with its percentages will be calculated for these variables.

--	---

